**Customized Impressions in Dental Implants - Soft Tissues Changes**

**NCT03496428**

**March 25th 2019**

## Study Protocol with Statistical Analysis Plan

### 2.1 | Patient selection

This clinical study was conducted in full compliance with the Helsinki World Medical Association Declaration and its most recent amendments, being approved by the local ethics committee and registered at the U.S. National Library of Medicine ClinicalTrials.gov website under the reference number NCT03496428.

The patients were chosen according to the following criteria: be at least 18 years of age; have at least one implant in the anterior maxilla with the indication for rehabilitation with a definitive implant supported crown; have two mesial and two distal adjacent teeth to the implant and be rehabilitated with a provisional implant supported crown for at least 3 months. As this was a pragmatic trial undertaken in a private clinical setting, patients with active smoking habits and evidence of parafunctional habits (ie, bruxism) were not excluded. Each patient was thoroughly informed about the procedures and each signed an informed consent agreement before entering the study.

### 2.3 | Conventional impression method with coping customization, stone model fabrication, and digitalization

In the same appointment, following the conventional workflow method (Figure 1), the CIIC was obtained by a previously described indirect technique. Briefly, the provisional crown was attached to an implant analog and placed into a polyvinyl siloxane impression material matrix (Affinis Putty, Coltene, Altsttten, Switzerland). The mold was obtained and the provisional returned to the patient's mouth to avoid soft tissue collapse. The impression coping was attached to the implant analog and filled with composite resin (Supreme 3M flow, 3M ESPE, Saint Paul, Minnesota), which took the 3D shape of the provisional soft tissue emergence, thus obtaining a CIIC (Figure 3). It was hand tightened and the proper seating was confirmed by visual and X-ray verification.

A dual viscosity impression in one-step pick-up procedure was constructed using a polyvinyl siloxane material (Affinis Light Body Type 3, Putty soft Type 0, Coltene, Altsttten, Switzerland) in a standard plastic die lock tray (Single Use Perforated Impression Tray, Solo, J&S Davis, Stevenage, Herts, United Kingdom) prepared prior to loading into position. The impression was removed from the patient's mouth at least 2 minutes longer than the manufacturer's recommendation (2 minutes) and stored at 23°C for 8 hours. The impression was poured with type IV dental stone (Top Super Hard Stone, class IV light yellow, Sherahard-rock, SHERA

Werkstoff-Technologie GmbH & Co. KG, Lemförde, Germany) after mixing according to manufacturer instructions. The stone model was separated from the impression after 40 minutes, stored at laboratory temperature (21°C-23°C) for 24 hours with no exposure to sunlight, and then scanned with the extraoral scanner D2000 (3Shape, Copenhagen, Denmark) with 5-megapixel high resolution cameras, multiline technology, and color scanning, achieving accuracy up to 5 µm, thus creating a STL file, which was previously calibrated according to manufacturer's instructions. This digitalized model was considered the reference.

## 2.4 | 3D analysis

Two STL files were obtained from each patient and, to allow for blinding, an external operator provided the STL files named with the patient reference number followed by the letter A (reference) or B (measured), keeping the correspondence code in an opaque sealed envelope until the end of the study. The files were imported into a reverse engineering software Geomagic Design X (3D Systems, Rock Hill, South Carolina) where they were cut to the zone of interest with the “Split” tool, removing unnecessary information and submitted to the “Healing Wizard” to reduce the number of distortions and small artifacts that could influence analysis. The generated datasets were then imported into the point-cloud inspection software Geomagic Control X (3D Systems).

Software validation was performed as previously reported and repeated five times per scan (60 repetitions in total) to check software reliability, after which, virtual sagittal planes were created to guide the standardization of the locations of interest—through the cervicalapical axis of each of the five structures (four teeth and one implant), frontal planes over the mesiodistal axis of the implant and the two adjacent teeth, three transversal planes parallel between them in the four teeth, one at the gingival zenith and two others apically from the first with 1 mm spacing between them, and in the implant at emergence profile base level which was defined with a horizontal plane in the most apical identifiable point of the customized emergence profile, mucosal zenith, and in the middle of them. The locations were determined by the intersection between the described planes with the superimposed scans and the linear differences obtained by the 3D analysis program. The amount of deviation between methods was obtained by calculating the root mean square (RMS) by previously established methods.

To evaluate the trueness between conventional (reference) and digital (comparison) impression methods, RMS distances were determined on both the buccal and palatal sides of the teeth, at cervical, incisal and in the middle point between them in each tooth (Bc, Bm, Bi, Pc, Pm, and Pi) and in the respective soft tissues (Gbc, Gbm, Gbz, Gpz, Gpm, and Gpc), as shown in Figure 4A. In the interproximal area of the implant (mesial and distal sides, Mip and Dip), the same locations as in buccal/palatal were measured (Figure 4B). In total, 304 comparisons were performed in teeth's hard and soft tissues to assess trueness between methods.

To evaluate the soft tissue replication between methods in periimplant soft tissues, the locations were measured at emergence profile base level (epbl), at the zenith (z), and middle (m) on the different sides of the implant mucosa: the buccal of the buccal mucosa (Bbm), the palatine of the buccal mucosa (Pbm), the buccal of the palatine mucosa (Bpm), the palatine of the palatine mucosa (Ppm), and the mesial and distal mucosa (Mm and Dm, respectively) (Figure 4C,D), corresponding to 18 locations per patient, amounting to a total of 108

measurements. If the scans presented teeth with modifications, for prosthesis fabrication or distortions, the affected areas were not assessed.

For each location with the “3D Compare” tool an area of interest with at least 1 mm^2 was selected and used to measure the differences between methods, with three replicates performed per location. The analysis software automatically calculated RMS and the mean of the three replicates considered for statistical analysis.

For optimal 3D visualization, a colored map was created with negative (blue, showing the comparison scan going inwards) and positive values (red, going outwards), as shown in Figure 5. Specific parameters were set to the color scale, ranging from +1000 to -1000  $\mu\text{m}$  and the best results ranging between +100 and -100  $\mu\text{m}$ , highlighted in green. Values over or below the color scale's limits were presented in gray.

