## 2.5 | Statistical analysis

Although no studies employing this technique were found in the literature, from a study on direct and indirect techniques in CIIC22 we expected a mean difference of 1 mm. A statistical power analysis was performed to determine the number of patients with an equivalence study design. With an  $\alpha = .05$ , and a power of 0.80, the calculations revealed that at least six patients would be needed to be 95% sure that the limits of a two-sided 90% confidence interval would exclude a difference in means of more than 500  $\mu\text{m}$ .

Primary outcomes were defined as the variation in the RMS between the two methods in the hard (teeth) and soft (teeth and periimplant mucosa) tissues' measurements. Descriptive statistic (means and 95% confidence intervals) was performed on the studied parameters. Normality of distribution was tested by the Shapiro-Wilk Normality test and the Levene test was used to assess the equality of variance. According to the results, the nonparametric Mann-Whitney U and Kruskal-Wallis tests were used to compare RMS between methods in hard and soft tissues ( $\alpha = .05$ ). When performing multiple comparisons, the P-value was adjusted according to the Bonferroni Correction method.

Effect size between soft tissues' measurements (tooth vs implants) was calculated as Hedges'  $g$   $\pm$  95% confidence interval as a result of different sample sizes. Effect size was considered as small (<0.3), moderate (0.3–0.8), or large ( $\geq 0.8$ ) effect. The level of significance was set at .05. All calculations were carried out with statistical software (SPSS 25.0, SPSS Inc., Chicago, Illinois).

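### Peri-implant RMS mixes soft-tissue shape with technical error, and section 2.5 never contrasts it with the same patient's enamel

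*Combined protocol and SAP*

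**What the plan says.** - **Reference.** Section 2.3 takes the desktop scan of the poured stone model as the standard: "This digitalized model was considered the reference". The comparison surface is the intraoral scan of section 2.2.
- **Measure.** Section 2.4: "The amount of deviation between methods was obtained by calculating the root mean square (RMS) by previously established methods". The scans are superimposed, and the sites are then located: "The locations were determined by the intersection between the described planes with the superimposed scans". Neither the alignment method nor the alignment region is stated.
- **Use in mucosa.** "To evaluate the soft tissue replication between methods in periimplant soft tissues, the locations were measured at emergence profile base level", at 18 sites per patient.
- **Use in teeth.** Hard-tissue RMS is taken at six sites on each of four neighbouring teeth, with gingival sites alongside, and is assigned to trueness. Modified or distorted areas are not assessed.
- **Outcomes and analysis.** Section 2.5: "Primary outcomes were defined as the variation in the RMS between the two methods", in hard tissue (teeth) and soft tissue (teeth and peri-implant mucosa). It plans means with 95% CIs, Mann-Whitney and Kruskal-Wallis tests, and a Hedges' g for tooth versus implant soft tissue.
- **Error figures.** Only one is given, for the desktop scanner: "multiline technology, and color scanning, achieving accuracy up to 5" µm.

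**The concern.** RMS is non-negative, so independent technical error does not cancel; it raises the level. A peri-implant RMS above zero may reflect mucosa that differs between the two workflows, or scanner, impression, stone and registration error, or both. Enamel cannot change shape within one appointment, so its RMS shows how far the two scans disagree where the surface is rigid. The plan collects this for every patient but does not set it against that patient's mucosa. The one tooth-versus-implant effect size uses gingiva, which is not rigid.

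Without a within-patient contrast, the results cannot show whether mucosa deviates more than a rigid surface in the same scan pair. With six patients, one poor registration could noticeably raise the average mucosal RMS.

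**Working it through.** **1. Inputs and counts.** The plan's own counts agree on the number of patients: 108 / 18 = 6 from the peri-implant sites, and 60 / (5 × 2) = 6 from the software check at two scans per patient. Enamel sites number at most 6 × 4 = 24 per patient. The documents give no RMS values and no overall workflow error, so the floors of 50, 100 and 150 µm below are assumptions. The ±100 µm green band in section 2.4 is a colour-map setting, not an error estimate.

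**2. What the planned repeatability checks cover.** The software check and the three replicates per location re-measure existing files. No scan, impression or pour is repeated, so neither captures workflow or registration error.

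**3. Effect of a floor, and of two ways to remove it.** Assume independent components, so that raw RMS = √(tissue² + floor²). Linear subtraction gives raw − floor. All values are in µm; percentages are bias relative to the tissue value.

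| Floor | Tissue | Raw RMS | Bias of raw | Raw − floor | Bias after subtraction |
|---|---|---|---|---|---|
| 50 | 0 | 50 | – | 0 | – |
| 50 | 100 | 112 | +12% | 62 | −38% |
| 50 | 200 | 206 | +3% | 156 | −22% |
| 100 | 0 | 100 | – | 0 | – |
| 100 | 100 | 141 | +41% | 41 | −59% |
| 100 | 200 | 224 | +12% | 124 | −38% |
| 150 | 0 | 150 | – | 0 | – |
| 150 | 100 | 180 | +80% | 30 | −70% |
| 150 | 200 | 250 | +25% | 100 | −50% |

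Read as a magnitude, linear subtraction is further from the tissue value than raw RMS in five of the six rows with non-zero tissue deviation. It is exact only when that deviation is zero. The paired difference therefore answers whether there is any excess over a rigid surface, not how large the tissue component is.

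**4. Quadrature removal.** √(observed² − floor²):
- observed 100: 87 with floor 50, 66 with floor 75, 0 with floor 100;
- observed 200: 194 with floor 50, 173 with floor 100, 132 with floor 150;
- observed 500: 490 with floor 100, 477 with floor 150, a reduction of 2% and 5%.

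**5. The planned hard/soft test.** Section 2.5 does not state the unit of analysis. If locations are pooled as independent, pairing and clustering within patients are lost. This was simulated with six patients, 24 enamel and 18 mucosa sites each, and no average difference between tissues. On the log scale the assumed SDs were 0.3 between patients and 0.4 between locations; 3,000 runs were made at a nominal 5% level.

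| Patient-by-tissue SD | Pooled Mann-Whitney rejects | Paired t on patient means rejects |
|---|---|---|
| 0 | 2.3% | 5.2% |
| 0.3 | 42.5% | 4.4% |
| 0.6 | 57.8% | 5.5% |

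**6. Precision with six pairs.** The 95% CI half-width is t(0.975; 5) / √6 = 2.571 / 2.449 = 1.05 SDs of the paired differences. A two-sided 5% paired t-test has 80% power only for a standardised difference of about 1.43. The smallest two-sided exact signed-rank P-value is 2 / 2⁶ = 0.031.

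**The case against.** **The aim is to compare two workflows.** The body of the plan speaks of deviation and replication between methods, and for that question scanner and stone error belong to the quantity of interest. This stands. A reader might infer from the title, "Customized Impressions in Dental Implants - Soft Tissues Changes", that the plan equates RMS with tissue change, but the wording appears only there, and the plan proposes no patient-by-patient reading of tissue collapse. Raw RMS is a legitimate outcome.

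**Enamel RMS is not ignored.** A reader might infer that it is. In fact it is a primary outcome, is described with means and 95% CIs, and enters the hard/soft tests. What is missing is the pairing within patient.

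**Enamel is not a proven common floor.** This also stands. If the scans were fitted on teeth, enamel RMS would be minimised by construction. The implant site also has steps that enamel lacks, namely coping customisation and seating. The documents therefore do not support treating enamel RMS as pure workflow error shared by every peri-implant site, demoting hard-tissue RMS to a mere control, or resting all soft-tissue conclusions on the excess.

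**Raw RMS is conservative for equivalence.** If the 500 µm margin is applied to RMS, technical error makes agreement harder to claim, whereas subtracting enamel makes it easier. Correct, and near 500 µm the effect is small. The paired difference should not replace raw RMS against that margin.

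**Conclusion.** The gap is real but narrow. Peri-implant RMS is a composite, and section 2.5 contains no within-patient contrast between mucosa and enamel, although both come from the same superimposition. The unpaired tests do not fill that gap, nor does the Hedges' g against gingiva.

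The size cannot be read from the documents. Under quadrature and the assumed floors, the composite matters at deviations of about 100 to 200 µm and little near 500 µm. The false-positive rates for the pooled rank test depend on location-level pooling and on the assumed SDs; they illustrate a mechanism and do not predict this trial's error rate. The consequence is for how soft-tissue results may be described. It does not invalidate raw RMS as a measure of disagreement between the workflows.

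**What to change.** In section 2.5:

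1. For each patient, average RMS over the peri-implant mucosa sites and over the unmodified enamel sites of the same superimposition. Report the paired difference with its mean and 95% CI over the six patients, beside the raw RMS.
2. Use this contrast, rather than the unpaired hard/soft test, as the evidence on whether mucosa deviates more than a rigid surface. Describe it in those terms, not as tissue change in µm.
3. If a magnitude is wanted, give √(implant² − enamel²) per patient as a sensitivity analysis, with a stated rule for patients whose enamel RMS is the larger.
4. Keep raw RMS and hard-tissue RMS as primary outcomes.

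In section 2.4, state the alignment region. Note that if alignment was on teeth, enamel RMS is a lower bound on error at the implant, and that enamel does not capture coping customisation or seating error.

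The cost is one derived variable per patient from data already collected. The difference adds some variance, the interval will be wide with six patients, and a patient without assessable enamel cannot contribute a pair.

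### Tooth areas with scan distortion are excluded under the same rule as areas modified for prosthesis work, so the primary tooth-site RMS may be selected on its own outcome; size and direction are unknown

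*Combined protocol and SAP*

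**What the plan says.** Section 2.4 gives one exclusion rule for tooth sites: "If the scans presented teeth with modifications, for prosthesis fabrication or distortions, the affected areas were not assessed". It does not define distortion, say in which of the two files it must appear, name who judges it, or say at what step.

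The same section describes three features that bear on the rule:

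- **File coding.** An external operator labelled the files A or B, "keeping the correspondence code in an opaque sealed envelope until the end of the study".
- **Repair.** The files were cropped and passed through an automatic healing tool "to reduce the number of distortions and small artifacts that could influence analysis", and only then imported into the inspection software.
- **Site placement.** "The locations were determined by the intersection between the described planes with the superimposed scans".

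On numbers, it reports: "In total, 304 comparisons were performed in teeth's hard and soft tissues to assess trueness between methods". Section 2.5 makes the RMS between methods in tooth hard tissue, tooth soft tissue and peri-implant mucosa the primary outcome. It also plans a Hedges' g for tooth against implant soft tissue. Section 2.3 makes the digitised stone model the reference.

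**The concern.** The tooth sites are there to measure how far the digital scan departs from the conventional one. Prosthesis work changes the object being scanned, so a deviation at such a site says nothing about the impression method. A distortion may be a failure of the impression or scan itself, and so part of what is being measured. If such areas are dropped because they look wrong, the sites that remain have been chosen partly by the outcome.

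What is at stake depends on where the defect lies. If it is in the digital file and the area deviates more than the rest, the mean tooth-site RMS is too low and trueness looks better than it was. If it is in the stone reference, dropping the area removes reference error instead. Hedges' g would be touched only if gingival sites were among those dropped.

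**Working it through.** **1. Do the safeguards in section 2.4 close the gap?**

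- The A/B coding hides which method produced a file. It does not hide where two surfaces disagree.
- The planes standardise where a site lies, but they are intersected with scans that are already superimposed. The rule does not say that distortion was judged before that step.
- The healing tool is an earlier and separate filter. The exclusion rule acts on whatever remained after it.

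None of the three prevents a measurable distortion from being excluded after the deviation could be seen. Equally, none shows that this happened.

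**2. Can the number of excluded areas be recovered from the 304 comparisons?**

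*Patients.* Peri-implant measurements: 108 / 18 per patient = 6. Software repetitions: 60 / (5 per scan × 2 scans per patient) = 6. The two routes agree, and 18 × 6 = 108 is complete, so no loss is visible at the implant.

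*Tooth grid from the text.* Section 2.1 requires patients to "have two mesial and two distal adjacent teeth to the implant", which makes 4 teeth. Section 2.4 names 6 hard-tissue and 6 soft-tissue locations per tooth. So 4 × 12 × 6 = 288.

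*Comparison with the stated total.* 304 − 288 = 16, so the stated total is above the grid in the text, not below it. Section 2.4 also describes sites "In the interproximal area of the implant", but their number per patient depends on a figure that is not shown. Either 304 includes at least 16 of them, or no loss can be inferred from it.

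*Divisibility.* 304 / 6 = 50.67, which is not whole. If all six patients had the same planned grid (an assumption), the next multiple of six is 306, so at least 2 sites were lost (2/306 = 0.7%). Assuming 6 or 12 interproximal sites per patient:

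| Assumed interproximal sites per patient | Planned sites | Shortfall from 304 |
|---|---|---|
| 6 | 288 + 36 = 324 | 20 (6.2%) |
| 12 | 288 + 72 = 360 | 56 (15.6%) |

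Even on these grids, the whole shortfall could be prosthesis-modified areas, which are validly excluded. The stated 304 therefore cannot be reproduced, and it says nothing about distortion.

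**3. What could the effect be? (Purely illustrative.)**

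Let q be the share of lost sites that were lost to distortion, and k the ratio of their RMS to that of the other sites. With w = q × lost / (304 + q × lost), the proportion by which the mean is understated is 1 − 1/(1 + w(k − 1)). A negative value means overstatement.

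Example: 324 planned, q = 1, k = 1.5. Then w = 20/324 = 0.0617, and 1 − 1/(1 + 0.0617 × 0.5) = 3.0%.

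| q | k | 306 planned | 324 planned | 360 planned |
|---|---|---|---|---|
| 0, any k | – | 0% | 0% | 0% |
| any q | 1 | 0% | 0% | 0% |
| 0.25 | 1.5 | 0.1% | 0.8% | 2.2% |
| 0.25 | 0.5 | −0.1% | −0.8% | −2.3% |
| 1 | 1.5 | 0.3% | 3.0% | 7.2% |
| 1 | 0.5 | −0.3% | −3.2% | −8.4% |

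The planned grid, q and k are all assumed. The table shows how the answer depends on them and is not an estimate for this trial.

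**The case against.** The rule is triggered by what the scans showed on the teeth, not by a large deviation. The files were cropped and healed in separate software before inspection, so defects could have been noticed before any superimposition. Nothing says that the colour map of deviation was used to exclude areas. The wording may mean only teeth that were altered or data too poor to measure, and for those, exclusion is proper. The same holds for a defect in the stone reference. What remains is measurable distortion in the digital file, and no such area is documented. Attribution is also limited: the stone model is the only reference, so for some defects nothing can tell which file is wrong.

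Most of this stands. It removes any claim that loss occurred, any claim about size or direction, and any demand that every defect be assigned to one file. It does not remove the fault in the rule. Distortion is undefined, its timing is unstated, and a measurable distortion falls under the rule as written.

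A reader might infer from 304 that sites were lost to distortion. The text does not support that: 304 exceeds the 288 tooth sites it describes, and any shortfall needs an assumed interproximal grid.

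**Conclusion.** The point holds as a fault in the exclusion rule: followed as written, it can remove part of the deviation that the primary outcome measures. Confidence is medium, because the documents show neither whether any area was excluded for distortion nor what its RMS was. The effect may be zero. Understatement of tooth-site RMS is plausible if the defect is in the digital file and deviates more than other sites, but neither size nor direction can be established.

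Two stronger readings are tempting and unsupported. One is that the reported trueness is too favourable, which would need both a documented loss and a known direction. The other is that the comparison with the 500 µm margin or the tooth-versus-implant Hedges' g is overturned. Nothing in the documents shows the first, and the second part would need gingival sites to be among those excluded, which is not shown either.

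**What to change.** Limit automatic exclusion to areas physically modified for prosthesis fabrication or not measurable, identified on each file before superimposition and without sight of the deviation.

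The methods are written as already carried out, so rewording alone would not settle the matter. Using the existing STL files:

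- Repeat the tooth-site RMS analysis with measurable distorted areas included, and show it beside the analysis without them. Repeat Hedges' g if gingival sites are affected.
- Report the number of excluded areas by reason.
- Where a defect is visibly in one file, say which. Otherwise mark it as not attributable.

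The cost is modest re-measurement, with no new patients or visits. The added analysis will be noisier and may carry some reference-model error. If no area was left out for distortion, one sentence saying so closes the point.
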